8.0 Data Handling

The Principal Investigator will act as custodian for the trial data. The following guidelines will be strictly adhered to:

- Participants data will be completely anonymised
- All anonymised data will be stored in a secure location on the University's servers and on a password-protected computer these will be in line with best practice as recommended in the University of Surrey Research and Information Governance policies.
- All trial data will be stored and archived as indicated by The Medicines for Human Use (Clinical Trials) Amended Regulations 2006.
- When a subject does not meet the inclusion criteria, all questionnaires and collected data will be destroyed.
- As part of the collaboration agreement with the Federal University of Goias, Brazil, all data collected in both countries will be shared between the two institutions.

9.0 Publication policy

The results of the study will be reported and disseminated to the scientific community via peer-reviewed journals and international conferences. The general public will be engaged via the release of results to the local and national media, relevant charities and community networks and an invited talk at the University.

10.0 Finance

Full funding to conduct the D-SOL Study is provided by the Science Without Borders Program through the National Counsel of Technological and Scientific Development of Brazil (CNPq).

Preferred method of contact: Phone Email Post
HEALTH AND LIFESTYLE
Height (cm): Weight (kg):
Are you currently receiving treatment for any medical conditions? Yes No
Medical condition: Treatment:

Are you on any medication prescribed by your GP or any other health care provider?

Yes No

1. Do you live in the UK?

Yes No

- If yes, please state the date you arrived: / /
- **2.** Please tick all medical conditions that apply:

Prior/ present history of coronary heart disease, angina, heart attack or stroke
Prior/present history of Type 1 and Type 2 Diabetes.
Prior/present history of Thyroid disease
Prior/present history of osteoporosis, osteopenia or other musculoskeletal disease
Prior/present history of haematological disease (except mild anaemia)
Prior/present history of malignancy
Prior/present history of a gastrointestinal disorder, such as Crohns Disease, Coeliac Disease or Irritable Bowel Syndrome.
Prior/present history of liver or kidney disease.

If yes, please specify:

- 5. Are you currently on a weight-reducing diet or other dietary restrictions (except vegetarianism)?

If yes, please provide details:

6. Have you been abroad on holiday during the past 6 months? Yes No

If yes, please specify where this was and the month this holiday was taken: Country of visit...... Month/year..... Month/year.... 6. Are you planning any holidays abroad during the next 12 months? Yes

No No

If yes, please specify where this visit is planned to be and when this holiday will be taken:

Country of visit..... Month/year Country of visit..... Month/year

7. Do you use sunbeds?

If yes, please state how often you use them:

Once a week	

Once a month

Less than 6 times per year

- Occasionally
- 8. Are you currently pregnant or planning a pregnancy during the next 12 months?
 - Yes 🛛 🗌 No

9. Are you currently breastfeeding?

10. Are you in menopause?

We are planning to see participants in the morning between 8.00am and 12.00 noon. Are there any particular day or days which would be best for you?

Thank you for taking the time to complete this questionnaire.

Participant signature:	Quest. No:	
Date://		\square

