2.2 Secondary Objectives

- (i) Analyze the difference regarding time and intensity of sun exposure between Brazilian women living in Brazil and Brazilian women living in the UK.
- (ii) Determine the prevalence of inadequate dietary Vitamin D intake in these women.
- (iii) Determine the prevalence of insufficient/deficient levels of vitamin D in these women.
- (iv) To elucidate the association between Vitamin D status and markers of calcium of calcium metabolism.
- (v) Examine the influence of latitude on vitamin D optimal levels.
- (vi) Analyze the influence of skin pigmentation on vitamin D optimal levels.
- (vii) Analyze if response to Vitamin D supplementation is dependent on initial vitamin D levels.
- (viii) Investigate the genetic and enzymatic mechanisms underlying the adolescents' response to vitamin D supplementation via genotyping for polymorphisms related to vitamin D metabolism and comparing the high and low responders to supplementation (Genetic Sub-Study).

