3.0 Experimental Design

Two controlled, randomized, double-blind clinical trials will be developed and undertaken (one in Brazil and the other in the UK) with an intervention period of 12 weeks.

A questionnaire to screen for the relevant inclusion and exclusion criteria (see section A) will be administered in order to select 80 Brazilian female subjects, aged 20 to 59 years, in each of the two countries. The women selected will be randomly divided into two groups: Placebo Group and Supplemented Group, the latter will receive 600UI UI of vitamin D.

The first clinical trial will run in the UK from October 2016 to March 2017 (autumn-winter) and then the second will run in Brazil from April 2017 to September 2017 (autumn-winter). After the analysis of the effect of vitamin D supplementation compared to placebo, the results obtained in the supplemented group will also be analysed according to the genotypes for SNPs in the VDR gene.

We have chosen 12 weeks (3 months) as the supplementation period as we consider this to be ample time for 25OHD levels to rise (half-life of 25OHD is 3 weeks) and this has been demonstrated to be an effective timeframe for supplementation of vitamin D in previous studies.

We have chosen 600IU to enable the study to be relevant to the new IOM US recommendations for vitamin D, which are currently the reference document used in Brazil, even though the Brazilian nutritional table remains with the daily intake recommendation of 200 IU, which was the IOM recommendation in 1997. Compliance will be checked by compliance interviews during the trial and by empty packaging count.

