3.3 Selection & Withdrawal of Participants

3.3.1 Inclusion Criteria

- Brazilian nationality
- Female
- Aged 20-59 years

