3.3.2 Exclusion Criteria

- Currently receiving treatment for medical conditions that are likely to affect vitamin D metabolism (osteoporosis therapy, anti-estrogens treatment, antiepileptic drugs, breast-cancer treatment)
- Hypercalcaemia (>2.5mmol/L) assessed and excluded at baseline

- Regular use of sun-beds
- Having a holiday trip one month prior to commencing the study or plans for a holiday trip for more than 4 weeks out of the country of residence within the study period.
- Use of vitamin supplements containing vitamin D (if the prospective participants agrees to stop Vitamin D supplementation to join the study, a wash-out period of 8 weeks prior to commencing the trial would be acceptable).
- Pregnant or planning a pregnancy during the study period.

If a participant is subsequently found to be ineligible for the study their screening questionnaire will be destroyed due to the questionnaire containing sensitive information.

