- Anthropometrics and blood pressure measured, and blood sample taken (serum 25OHD levels, 1,25-dihydroxy vitamin D, serum calcium, albumin, parathyroid hormone, C-terminal telopeptide (CTX) ≈25ml) with an additional ≈10 ml for genetic profiling and ≈15 for storage for future measurements of nutritional markers.
- Bioelectrical impedance analysis (BIA) for body composition.
- Dosimeter and 4-day food diary received from participant (sent to participant prior to appointment).

DNA profiling procedure - After 12 weeks RCT

• Selection of 48 participant samples encompassing the best and worst supplementation-responders in each group, subject to previous consent form participant. Vitamin D related genes will be genotyped in DNA isolated from the study blood samples, DNA will be extracted and vitamin D polymorphisms will be determined by University of Surrey's genetic labs.

A trained phlebotomist will take the blood samples required as part of the trial protocol. Medical cover will be available at all times.

Throughout the duration of the trial, the participants will be contacted via telephone on a fortnightly basis to discuss any issues with any adverse event and compliance and to maintain good communication with the participants. (Please see AE reporting form). In the case of a serious adverse event (SAE) this will be recorded (please see SAE reporting form) and we will report it to both the Sponsor (University of Surrey) and the Surrey Ethics Committee.

The final interview will be completed at the final study visit. Participants have also be asked to return any supplements that were missed to confirm compliance.

For University of Surrey participants: A peripheral quantitative computed tomography (pQCT) scan was performed on the participant's non-dominant forearm at the baseline visit, to measure volumetric bone mineral density at the 4% and 66% radial site. This will allow for separate measurements of trabecular vBMD and trabecular area (4% site) and cortical vBMD and cortical area (66% site), as well as strength strain index, a measure of bone strength. pQCT also measures bone geometry alongside bone density. Therefore the muscle cross sectional area can be determined, which is a measure of muscle force, to which bone strength is adapted to. One scan was performed at baseline only and effective exposure doses were between ~1.5-1.8uSv.

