7.0 Study Evaluation and Statistical Analysis

Statistical analysis will be undertaken with support from the University of Surrey statistical department. Data will be checked for normality using appropriate testing. Appropriate parametric/non-parametric analysis will be applied.

The database will be stored and analysed using SPSS ® version 13.0.

The descriptive analysis, including mean ± standard deviation, median and lower limit and higher will be held for all quantitative variables Data will be checked for normality using appropriate testing. Appropriate parametric/non-parametric analysis will be applied. Student t test or Mann-Whitney test, depending on the distribution of data, will be applied to evaluate differences between supplemented and placebo. For analysis between Brazil and UK groups an ANOVA test will be undertaken. Linear correlation, Pearson or Spearman, will be calculated in accordance with the presence / absence of normal distribution, respectively, between vitamin D intake, sun exposure, skin pigmentation and vitamin D serum concentration. Multiple linear regression analysis will be performed to determine the variants that influence blood concentrations of vitamin D. In order to determine whether supplemental response differs between genotypes, these will be separated into wild homozygotes, heterozygotes and homozygotes for the variant. In this approach, the results will be evaluated with the test ANOVA or Kruskal-Wallis, in cases of variables with normal distribution or not, respectively. To describe the relationship between food intake aspects and features biochemical independent of energy intake, intake values of nutrients of interest will be adjusted to energy in accordance with the method. Significance considered as standard will be 5%.

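### Section 7.0 states no analysis for objective (iv) and no adjusted comparison of PTH, CTX and calcium, although menopausal status is asked at screening in women aged 20 to 59

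*Combined protocol and SAP*

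**What the plan says.** Eligibility (3.3.1) is female, Brazilian and "Aged 20-59 years". Menopausal status is neither an inclusion nor an exclusion criterion, so pre- and post-menopausal women can both enrol. Question 10 of the Screening Questionnaire asks "Are you in menopause"; menopause is mentioned nowhere else in the text supplied.

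Objective (iv) in 2.2 is "To elucidate the association between Vitamin D status and markers of calcium of calcium metabolism". It does not name the markers. The blood-sample lists in 4.1, for both the baseline and the final visit, include "serum calcium, albumin, parathyroid hormone, C-terminal telopeptide (CTX").

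Section 7.0 lists these analyses:
- a t-test or Mann-Whitney test between supplemented and placebo women, with no covariates;
- an ANOVA between Brazil and the UK;
- correlations "between vitamin D intake, sun exposure, skin pigmentation and vitamin D serum concentration";
- a regression: "Multiple linear regression analysis will be performed to determine the variants that influence blood concentrations of vitamin D". Its outcome is blood vitamin D and no covariates are listed;
- an ANOVA or Kruskal-Wallis test by genotype;
- energy adjustment of nutrient intakes when diet is related to biochemical features.

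No item relates PTH, CTX or calcium to 25OHD. On allocation, 3.0 says "The women selected will be randomly divided into two groups: Placebo Group and Supplemented Group" and names no stratification factor.

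**The concern.** Objective (iv) is observational: it asks how 25OHD and the calcium-metabolism markers move together across women, so randomisation does not protect it. CTX is a bone-resorption marker, and an age range reaching 59 can mix women before and after menopause. If CTX or PTH shifts with menopause, a pooled and unadjusted association carries variance that has nothing to do with vitamin D. If 25OHD also differs between the two groups of women, part of the pooled association reflects menopause and could be read as a vitamin D effect.

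The comparison of these markers between arms raises a milder issue. Each has a baseline value, and the only two-group method in 7.0 does not use it. What is lost there is precision.

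**Working it through.** **1. Is there a figure in the plan to reproduce?** No. The one calculated figure, the sample size in 3.1, concerns 25OHD between arms and does not bear on this point. The documents give no share of post-menopausal women and no mean or SD for any marker.

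**2. What 7.0 provides for objective (iv).** The objective needs a marker and 25OHD in the same analysis. The listed correlations omit the markers. The regression makes 25OHD the outcome. The two-group, country and genotype tests compare groups and estimate no association. The energy adjustment concerns diet. So nothing is committed to for objective (iv), with or without menopausal status.

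**3. Illustration of size, on assumptions only.** Let p be the post-menopausal share, d1 the marker shift and d2 the 25OHD shift with menopause, both in within-group SDs. Assume no correlation within either group, and write v = p(1 − p).

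- Pooled spurious correlation: r = v·d1·d2 / √[(1 + v·d1²)(1 + v·d2²)]
- Marker variance due to menopause: v·d1² / (1 + v·d1²)
- False-positive rate: m = atanh(r)·√(n − 3), then Φ(−1.96 + m) + Φ(−1.96 − m). This takes the 5% level in 7.0 as two-sided; sidedness is not stated there.

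Assumed ranges, with CTX as the example: p from 0.1 to 0.3, d1 from 0.5 to 1.0, d2 from 0 to 0.5.

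| Case | p, d1, d2 | r | Marker variance | False-positive rate, n = 160 |
|---|---|---|---|---|
| No 25OHD difference | 0.3, 1.0, 0 | 0 | 0.21/1.21 = 17.4% | 5.0% |
| Low, with a 25OHD difference | 0.1, 0.5, 0.2 | 0.009/√(1.0225 × 1.0036) = 0.009 | 0.0225/1.0225 = 2.2% | 5.1% |
| Midpoints | 0.2, 0.75, 0.35 | 0.042/√(1.09 × 1.0196) = 0.040 | 0.09/1.09 = 8.3% | 7.9% |
| Worst corner | 0.3, 1.0, 0.5 | 0.105/√(1.21 × 1.0525) = 0.093 | 17.4% | 21.5% |

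The midpoint row uses the middle of the range for d2 where a 25OHD difference exists (0.2 to 0.5).

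**4. Dependence on sample size.** The 160 pools both countries (2 × 80). In the worst corner the rate is about 18% with 128 completers (160 × 0.8, the 20% drop-out in 3.1) and about 13% in one country of 80. Even there, r = 0.093 lies below the correlation needed for significance: about 0.16 at n = 160 and 0.22 at n = 80.

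**5. If only the marker shifts.** With d2 = 0 nothing spurious arises, but a true within-group correlation is divided by √(1 + v·d1²). That is √1.0225 = 1.01 at the low end and √1.21 = 1.10 at the high end, a dilution of about 1% to 9%.

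**The case against.** The strongest reply is that there is no faulty model here to criticise. Section 7.0 does not state any analysis of objective (iv), so it cannot be said to omit a covariate from one. This stands, and it is why the point is put as a missing commitment. Several stronger readings are tempting and are not supported:

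- **That the plan has decided to pool pre- and post-menopausal women for objective (iv).** Pooling is only what an unrestricted sample gives by default.
- **That menopausal status is used in no analysis.** The 25OHD regression has no covariate list, so age or menopause is neither in nor out. Adding it there would still not serve objective (iv), whose markers are not that regression's outcome.
- **That the protocol itself recognises oestrogen status as relevant**, because 3.3.2 excludes "osteoporosis therapy, anti-estrogens treatment, antiepileptic drugs, breast-cancer treatment". That list concerns treatments likely to affect vitamin D metabolism. It says nothing about natural menopause, PTH or CTX. The link from menopause to these markers is a general premise, not one taken from the documents.
- **That a false-positive rate near 21% is to be expected.** It needs all three assumptions at their extremes and both countries pooled.
- **That the trial's randomised result is compromised.** Randomisation protects comparisons between arms from systematic imbalance in menopausal status. Adjustment there is a matter of precision.

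It is also fair to say that question 10 is a single undefined self-report, taken by phone or email, and that complete answers are not assured.

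**Conclusion.** The point holds as a low-cost improvement. On the text alone, objective (iv) has no stated analysis, and the only stated method for comparing arms makes no use of the markers' baseline values or of menopausal status.

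Any bias is probably small and cannot be established from the documents. Under the assumed ranges the spurious correlation is 0 to 0.09. With 160 women pooled, the false-positive rate is 5% if 25OHD does not differ by menopausal status, about 8% at the midpoints and about 21.5% in the worst corner. These figures rest entirely on the assumed share and shifts, and they were worked with CTX in mind; PTH and calcium could shift less or not at all. What is affected is a secondary, observational objective and the precision of the marker comparisons. The randomised 25OHD comparison is not biased.

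**What to change.** In 7.0:

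1. Name the markers for objective (iv), and regress each of PTH, CTX and calcium on 25OHD with age, menopausal status and country. For 12-week values, add arm.
2. For these markers, replace the unadjusted t-test or Mann-Whitney comparison of supplement with placebo by ANCOVA on the marker's baseline value and menopausal status.
3. State how a missing or uncertain answer to question 10 will be handled.
4. Optionally, repeat the association models in pre-menopausal women alone as a sensitivity analysis.

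The cost is SAP wording. Beyond 25OHD, the association models use three degrees of freedom (age, menopausal status, country), or four with arm; the ANCOVA uses two beyond arm. No new measurement is needed. The adjustment is only as good as one self-reported screening item, which may be incomplete.
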